# **7. TRIAL TREATMENT / INTERVENTION**

# 7.1. Trial Treatments

### 7.1.1. Control/ Comparator group

Women assigned to the comparator (control) arm will receive the usual care provided for infant feeding within their locality. Women will receive routine maternity care which should include an offer of a routine antenatal visit from their health visitor; an offer to attend parent craft groups, which discuss infant feeding; written information about the national breastfeeding helpline and local breastfeeding support services which are generally given as part of routine care either by the community midwife or on hospital discharge. We have chosen localities that have an existing peer support service, but where peer support is not universally delivered proactively in the antenatal and postnatal periods. Peer support may be

available at a woman's request postnatally, often in a breastfeeding group; however, such services are only accessed by a minority of women. Therefore, usual care may include reactive peer support and breastfeeding support groups.

# 7.1.2. Planned ABA-feed Intervention

The ABA-feed intervention consists of proactive feeding support, underpinned by behaviour change theory and an assets-based approach in addition to usual care. The intervention delivers person-centred care and uses best evidence in terms of setting and frequency, duration and manner of support provision from the ABA-feed IFH. The ABA-feed intervention aims to be inclusive of all feeding methods (i.e. breastfeeding, formula or mixed feeding) and to provide support for all women. The theoretical underpinning of the intervention is described in section 1.2.3 and logic model is in appendix 1. A remote-only version will be delivered in the event of COVID restrictions.

Before the intervention commences, local teams and the local infant feeding lead will develop an 'assets leaflet' at each study site. This leaflet will be specific to the study areas and include information on local community 'assets' (including antenatal or postnatal groups, breastfeeding drop-in centres, details of local breastfeeding counsellors and baby groups) as well as details of national helplines and internet resources. The leaflet has space for the IFH to put their name and contact details. The assets leaflet will be emailed to each woman or they can access via a password protected link on the study website. If meeting in person, a hard copy will be given to them.

The ABA-feed intervention is delivered by existing trained breastfeeding peer supporters who have received additional training to deliver the ABA-feed intervention (see 7.1.3). They will be supported in their role and managed throughout their involvement by a local peer support manager or infant feeding co-ordinator, according to local practice.

The intervention will start at around 30 weeks' gestation and can continue up until 8-weeks postnatally. At around 30 weeks' gestation, the IFHs will contact women by telephone to arrange an antenatal meeting at a suitable location such as a children's centre or café, or at home if their peer support service allows this. Alternatively the meeting can take place remotely using a video-conferencing facility/WhatsApp/FaceTime etc., or over the telephone if women prefer. Women are welcome to include partners or family members in this and subsequent meetings. The purpose of this antenatal meeting is to talk about infant feeding and investigate the woman's 'assets' for infant feeding. An approach of 'narrative storytelling' will be used to produce a Friends and Family diagram that details the woman's friends/family members' experiences with infant feeding and expected quality of support, to facilitate reflection on future feeding relationships and sources of support. See Appendix 2 for an example Friends and Family diagram. At the antenatal meeting, IFHs will introduce the women to the assets leaflet, explain the range of support available for infant feeding, and swap contact details. A 'Let us know when you've had your baby' fridge magnet and maternity bag luggage label will be posted to the woman by the research team at 36 weeks of pregnancy, to encourage inclusion of the research team and the IFH on the list of people they would inform on the birth of the baby. There will be the possibility of posting a printed version of the assets leaflet at this point.

Following the antenatal meeting, the IFHs will be asked to call and/or text the women every two or three weeks during the pregnancy to encourage a strong rapport between the IFHs

and the women, in order to facilitate successful immediate engagement after birth. If it is possible, IFHs will be encouraged to offer to accompany women (antenatally) to a local breastfeeding group if the women plans to breastfeed, so women know how and where to access support for infant feeding once their baby is born.

Postnatally, IFHs will offer to contact the woman daily by text (or alternative social media platform such as but not limited to WhatsApp, Facebook Messenger, or FaceTime, or telephone call if preferred) until the baby is 2 weeks old, with less frequent contact until 8-weeks. In the feasibility study women expressed a preference for texts. Frequency of contact is according to women's preferences, for example, the need for infant feeding support may reduce if a woman is fully formula feeding. The IFH will offer information about formula feeding preparation and practices, including responsive formula feeding following infant feeding cues.

When a woman ceases to have support from her IFH she follows her personal choice of infant feeding pathway drawing on local feeding pathway resources.

In the feasibility study women who had a pre-term birth sometimes missed out on the antenatal component. On these occasions, we will encourage a postnatal meeting to co-produce the Friends and Family diagram, and to give women the assets leaflet and encourage women to draw on available resources as needed.

# 7.1.3. Training

In the feasibility study IFHs were provided with six hours of training plus a study folder. We propose that training should be increased to address some components in more detail. To facilitate sustainability, we will use a train the trainer model. We will train the infant feeding and peer support leads at each site and provide video clips of examples of the intervention components that can be used to train IFHs and watched again by any IFH wanting to consolidate their learning. This training will be delivered remotely over several sessions. These local peer support service leads will then train the peer supporters locally to become IFHs. The aims of the training are (1) to promote competence and confidence in delivering the ABA-feed intervention, and (2) to facilitate understanding of the ABA-feed study overall. The training will be interactive and will involve watching simulations and role-play of contact with women as well as group-based learning activities. These training sessions will also be delivered remotely or in-person, according to circumstances.

Building on the findings of the feasibility study we propose to explain in detail the two core BCTs to IFHs which should be delivered to every woman social support and restructuring the social environment, focusing particularly on how these can be delivered in line with an assetbased and women-centred approach. BCT training will explicitly introduce the concept of using specific techniques and draw on good practice examples from the feasibility study.

The training will include:

- (i) study information;
- (ii) overview of the intervention including recommended contact frequency, explanation of the assets-based approach (seeing the *woman* (not the IFH) as the solution and viewing relationships as assets together with available

*community support)*, woman-centred approach, infant-feeding approach, BCTs and how the intervention components are backed-up by evidence;

- (iii) completion of the family and friends diagram and how it can be used in future contacts;
- (iv) watching simulated conversations of parts of the antenatal meeting followed by modelling an assets-based approach and BCTs by role play;
- (v) supporting mothers using formula milk
- (vi) understanding boundaries, safeguarding and referral to health care professionals.

The trained IFHs will complete a form to confirm that they have completed all the training components, this will be held at BCTU for monitoring.

# 7.2. Cessation of Treatment / Continuation after the Trial

The participant may discontinue trial intervention at any point if they choose to or if their healthcare team feel that continued trial intervention is inappropriate.

Any participants who decide to discontinue the trial intervention will continue on their ongoing standard of care pathway.

# 8. OUTCOME MEASURES AND TRIAL PROCEDURES

# 8.1. Internal Pilot stage Trial Outcomes

An embedded internal pilot will run in all units over a period of six months to assess site recruitment and rates of recruitment of women into the trial. Pre-specified progression criteria have been agreed as follows:

	Red	Amber	Green	
Number of sites open	<10	11-14	15	
Number of IFHs trained	<107 (<80% planned)	107-133 (80-99% planned)	134 (100% planned)	
Cumulative recruitment target	<546 (<20% sample size)	546-818 (20-29% sample size)	819 (≥30% sample size)	
Actions	Discuss with TSC and consider stopping trial	Discuss with TSC strategies for improvement and consider changes to processes including opening further recruiting centres/ sites	Continue	

In the light of the ongoing uncertainties during the COVID-19 pandemic and ongoing disruption to maternity care and Research and Development Services, additional actions (e.g. increasing number of recruiting centres opened and/or recruiting additional peer supporters at each site) to support recruitment may be necessary to achieve the pilot targets in an appropriate timeframe.

# 8.2. Main Trial Outcomes

#### 8.2.1. Primary Outcome

Any breastfeeding at 8-weeks post birth, defined in accordance with the UK Infant Feeding Survey 'as infant being breastfed (including being given expressed breastmilk), within the past 24 hours, even if they are also receiving infant formula, solid food or other liquids'.

This will be measured by self-report in the 8-week questionnaire (or subsequent text message for non-responders), with missing data supplemented from health visitor records (women report their feeding method to their health visitor at the 6-8 week check as part of the Healthy Child Programme in England, Healthy Child Wales Programme and Child Health Surveillance Programme in Scotland which provide routine data to varying levels of completeness).

### 8.2.2. Secondary Outcomes

Secondary outcomes will be measured from the 3-day postnatal text message, 8-, 16-, and 24-weeks questionnaires

### 8.2.2.1. Clinical

- Breastfeeding initiation defined as baby put to the breast, even if this was on one occasion only and includes giving babies expressed breast milk.
- $\circ$   $\,$  Any breastfeeding at 16-weeks post birth.
- Any breastfeeding at 24-weeks post birth.
- Exclusive breastfeeding at 16-weeks post birth (defined in accordance with the WHO definition of infants who received only breast milk during the previous 24 hours);
   "Exclusive breastfeeding is defined as the baby receiving no other food or drink, not even water, except breast milk (including milk expressed), but allows the infant to receive oral rehydration solution, drops and syrups (vitamins, minerals and medicines)."
- Exclusive breastfeeding at 24-weeks post birth.
- Time to cease exclusive feeding with breastmilk, up to 16-weeks.
- $\circ$  Time to cease feeding with any breastmilk, up to 16-weeks.
- Maternal anxiety at 8-weeks post birth (measured by the Generalised Anxiety Disorder Assessment (GAD-7))
- Maternal anxiety at 16-weeks post birth (measured by the GAD-7)
- Maternal health related quality of life at 8-weeks (measured by the EuroQol (EQ-5D-5L))
- Maternal health related quality of life at 16-weeks (measured by the EQ-5D-5L)
- Maternal social support at 8-weeks post birth (measured by Medical Outcomes Study (MOS) Emotional / Informational Support domain;)
- Maternal social support at 16-weeks post birth (measured by MOS Emotional / Informational Support domain;)
- The following maternal self-reported formula feeding practices (how formula is prepared) (using questions from the UK Infant Feeding Survey;) at 8-weeks post birth and 16-weeks post birth:
  - Making one feed at a time
  - Correct water temperature

- Adding formula powder before water
- $\circ$  Making up formula when needed when out of the home
- Keeping milk chilled when out of the home
- Making formula with hot water when out of the home
- Sterilising bottles using recommended methods
- Maternal use of support for infant feeding (e.g. national breastfeeding helpline; peer support; breastfeeding groups) at 8-weeks post birth and 16-weeks post birth.
- Diagnosis of tongue tie in baby and whether treated, measured at 8-weeks post birth.
- Any infant hospital admission up to 16-weeks post birth associated with feeding mode in the postnatal period, e.g. feeding difficulties, failure to gain weight, jaundice, respiratory or gastrointestinal infection in infants.

#### 8.2.2.2. Economic

At 8 and 16-weeks post birth from the questionnaire:

- EQ-5D-5L instrument at baseline, 8-weeks and 16-weeks to examine outcomes both overall and with particular focus on the stress and anxiety domain
- use of feeding support from formal and voluntary sector;
- postnatal consultations with midwives, health visitors, and GPs,
- attendances at A&E / casualty
- hospital admissions for either mother or baby that are associated with feeding mode in the postnatal period, e.g. feeding difficulties, failure to gain weight, jaundice, respiratory or gastrointestinal infection in infants, or mastitis in mothers.

# 8.3. Schedule of assessments

An overview of the schedule assessments for the ABA-feed trial is given below in Table 1.

#### 8.3.1. Baseline data

Women who are recruited in-person will complete a paper version of the baseline questionnaire, it will be entered into the study database by the recruiting centre/Hub centre staff or Trial office. Women recruited remotely will complete the baseline questionnaire online via a web-link emailed to them by the researcher at recruiting centre/Hub. If they do not have internet access a paper version will be posted to them to be returned with pre-paid addressed envelope to the recruiting centre/hub research staff or Trial office.

At recruitment women will be asked to provide demographic characteristics (date of birth, ethnicity, highest level of qualification, relationship status, postcode (for calculation of Index of Multiple Deprivation quintile), work status), how they were fed as a baby, thoughts about how they might feed their baby, MOS social support scale, GAD-7 and EuroQol EQ-5D-5L.

#### 8.3.2. Follow-up assessments

All other follow-up assessments will be managed directly from the ABA-feed Trial Office. There will be no subsequent assessments following stillbirth or infant death.

• An automated text message will be sent at 3-days postnatal, with responses by text message, which will be directly linked with the trial database;

- An emailed link to an online questionnaire will be sent at 8-, 16- and 24-weeks to all women willing to complete questionnaires online;
- A paper questionnaire will be sent, with pre-paid addressed return envelope, at 8-, 16- and 24-weeks to all women who elected to complete questionnaire on paper; this will be returned to the ABA-feed Trial Office and entered by a data manager or delegated staff member;
- Telephone follow-up will be undertaken for participants who elected for this form of follow-up (BCTU / Hub).

Hub and recruiting centre staff will collect 8-week feeding records from health visiting records.

	Concention	Describer	Text			14/2 - 1- 24
	Screening	Baseline	day 3	March Oreart	Mark 10	Week 24
	(before	(before	post	Week 8 post	Week 16	post birth
	36/40)	36/40)	birth	birth	post birth	(-14 to
	weeks	gestation	(+ 10	(+ 30 or –	(+ 30 or –	+10 days)
Visit	gestation	weeks	days)	14 days)	14 days)	
Eligibility check	x					
Valid informed consent	x					
Relevant obstetric history taken	x					
Demographic data	x					
Infant feeding plans	x					
Randomisation		x				
Infant feeding status			x	x	x	X
Details of mode of birth				x		
Health & social resource use				x	x	
Infant feeding difficulties				x		
Self-reported formula feeding						
practices				x	x	
EQ-5D-5L		x		x	X	
GAD-7		x		X	X	
MOS social support		x		x	x	
Infant deaths		x	x	X	x	

#### Table 1: Trial participant schedule of events and summary of assessments

# 8.4. Changes in Levels of Participation

Participants should be aware during the consent process that they can freely discontinue participation from the trial (or part of) at any time, without providing a reason.

A participant may wish to cease to participate in a particular aspect of the trial.

The changes in levels of participation within the trial are categorised in the following ways:

- The participant would like to continue with the trial intervention but would like to withdraw consent from any further data collection (i.e. only data collected prior to the withdrawal can be used in the trial analysis)
- The participant would like to continue with the trial intervention but is not willing to be followed up in any way for the purposes of the trial but is willing for routine data to be used to collect the primary outcome.
- The participant would like to discontinue the trial intervention, but is willing to be followed up in accordance with the schedule of assessments (i.e. the participant has agreed that data can be collected and used in the trial analysis)
- The participant would like to discontinue the trial intervention and is not willing to be followed up in any way for the purposes of the trial and for no further data to be collected (i.e. only data collected prior to the withdrawal can be used in the trial analysis)
- The participant would like to discontinue the trial intervention and is not willing to be followed up in any way for the purposes of the trial but is willing for routine data to be used to collect the primary outcome.

The details of changes of levels in participation within trial (date, reason and category of status change) should be clearly documented in the source documents.

Women who have pregnancy loss, stillbirth or infant death will not be approached for further follow-up. For further information, see section 9.2.

# 9. ADVERSE EVENT REPORTING

# 9.1. Adverse Event Recording

There is no reason to assume that this trial will lead to an excess of adverse events; no related harms have been reported in the extensive literature on this intervention  which is provided outside the NHS. Infant feeding support is already part of standard care. NICE recommends breastfeeding peer support for women in low income households, and recommends the provision of written information about local breastfeeding support groups and how to prepare and store formula milk safely, both of which are components of the ABA-feed intervention. Therefore, no adverse events will be collected for this trial.

A significant proportion of babies are admitted to hospital in the first three months of life  (169 per 1000 live births), including 38 per 1000 live births for physiological jaundice, gastroenteritis and feeding difficulties. We therefore expect approximately 462 babies to be admitted to hospital in the first 3-months of the trial.

Given the low risk nature of the intervention an expedited reporting of Serious Adverse Events (SAEs) will not be required. However, during follow-up we will systematically collect self-reported data from participants regarding admissions to hospital by infant and mother requiring an overnight admission and the reasons for this. We will also capture whether there have been any infant deaths and cause of death. These will be reviewed by the DMC at regular intervals.

Should we receive any reports from participants, feeding teams or health care professionals of an infant death in which an IFH was the last health care professional/feeding supporter to have been in contact with the woman prior to the infant's death, then this will be investigated by the local PI and assessed by the CI for relatedness.

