# DEFINITIONS

Term	Abbreviation	Description			
Policies	POL	Policies are developed to describe the approach of the University of Birmingham (UoB) on areas that are heavily regulated. Policies may also be developed when there is ambiguity in how regulatory requirements should be implemented in the QMS or when procedures to be captured in the QMS address areas controversial within the UoB at the time of implementation. Policies explain why the UoB has its procedures, especially when they seem to deviate from the regulatory requirements. Policies should be read in conjunction with the relevant SOP. Policies that are not part of a Quality Manual are coded up as 'POL'.			
Quality Control Documents	QCD	Quality Control Documents can be instructions forms, templates or checklists. They are developed to share best practices, promote standardisation to guarantee quality standards are maintained and reduce resources otherwise needed to develop similar documents. Unless indicated otherwise in the relevant SOP, QCDs are not mandatory and and designed to be an optional aid to UoB staff.			
Quality Management System	QMS	A Quality Management System (QMS) is a system that includes procedures and policies to describe how certain tasks should be performed and that encapsulate any standards and/or regulatory requirements that may apply to those tasks. By			

		adhering to the Quality Management System, the user and the UoB will be assured that applicable regulations are adhered to.	
Standard Operating Procedures	SOP	Standard Operating Procedures are detailed written instructions to achieve uniformity in the performance of a specific function. They define tasks, allocate responsibilities, detail processes, indicate documents and templates to be used and cross- reference to other work instructions and guidance or policy documents. They are standards to which the UoB may be audited or inspected.	
Adverse Event	AE	Any untoward medical occurrence in a participant or clinical trial subject participating in the trial which does not necessarily have a causal relationship with the intervention received.	
Related Event		An event which resulted from the administration of any of the research procedures.	

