At 8-, 16- and 24-weeks post birth a web-link for completion of an online questionnaire with the option to request a paper version will be sent; women who requested paper questionnaires at baseline will be posted a questionnaire by the recruiting centre/ hub or the ABA-feed Trial Office. The ABA-feed Trial Office will transcribe the data from completed paper CRFs to the online database when the CRF is returned to the Trial Office.

Non-responders will be sent a text question about feeding and a reminder to complete the questionnaire. Missing 8-week feeding method will be sought by researchers from routinely collected data, as in the ABA feasibility study.

The database system will include data validations to improve data quality (e.g. to prevent nonsensical dates or numerical values). Changes to the data, on the system, will be made by ABA-feed Trial Office staff and will be documented and attributable where the Trial Office transcribes this data.

On-site monitoring will, for the most part, be triggered by poor recruitment or poor data returns. CRFs may be checked against the source data where on-site monitoring is conducted and must be available for verification.

A bespoke password protected database will be developed to record details of contacts between a woman and the IFH and actions taken (e.g. mode of contact and any advice to seek further help). It will have a function to enable a photo of the woman's family and friends diagram to be securely stored. The family and friends diagram will not include any personal identifiers (woman's first name only). The database will only include the woman's trial number and initials. The record will only be visible to the local IFH team (IFH manager and IFHs in the locality to enable cross cover of support if needed) and the ABA-feed team at BCTU.

Audio recordings of qualitative interviews will be collected on encrypted recorders and sent securely for transcription. Records will be sent securely to the University of Birmingham and stored as password protected documents on secure University of Birmingham Servers.

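### Section 9.1 states a relatedness assessment only for infant deaths where an infant feeding helper was the last professional or supporter in contact; other deaths after helper support get DMC review but no stated relatedness judgement

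*Protocol*

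**What the plan says.** Section 9.1 sets up three layers of safety information.

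- **General adverse events.** The section argues that the intervention is low risk and concludes: "Therefore, no adverse events will be collected for this trial". Expedited SAE reporting is also waived.
- **Admissions and deaths.** Overnight admissions of mother or infant are collected by self-report. For deaths: "We will also capture whether there have been any infant deaths and cause of death". The next sentence reads: "These will be reviewed by the DMC at regular intervals". Neither sentence depends on who was last in contact with the woman.
- **Case-level assessment.** If a report is received of "an infant death in which an IFH was the last health care professional/feeding supporter to have been in contact with the woman", "then this will be investigated by the local PI and assessed by the CI for relatedness".

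Four other places bear on the point. The Definitions table describes a related event as "An event which resulted from the administration of any of the research procedures". Section 7.1.3 lists "understanding boundaries, safeguarding and referral to health care professionals" among the IFH training topics. Section 10.4 provides a database to "record details of contacts between a woman and the IFH and actions taken". Section 9.2 asks for every infant death to be passed to the Trial Office, for the stated purpose of preventing distressing follow-up requests.

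**The concern.** The third layer is the only place where the protocol states that somebody judges whether a particular death was related to the trial. Entry to it depends on the order of contacts, and that is a poor proxy for possible relatedness. A woman can be supported by an IFH while her baby feeds poorly and then be seen by a midwife or in hospital. If the baby dies after that contact, the IFH was not the last in contact and the stated route does not apply, however closely the IFH had been involved.

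At stake is what the trial can say at the end. A report of no related infant deaths would rest partly on a screen that left some deaths after IFH contact without a relatedness judgement. With no general adverse event collection, nothing else stated in the protocol would supply that judgement.

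**Working it through.** The point rests on the text. One figure in 9.1 was checked, and the rest is a comparison of the provisions.

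**1. The section's own figure.** Section 9.1 gives 169 admissions per 1,000 live births in the first three months and expects about 462 admitted babies. With the 2,730 women of section 13.1: 2,730 × 0.169 = 461.4, which agrees with the stated figure to within rounding. The point does not depend on this number.

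**2. Who meets the trigger.** Applying 9.1 to possible sequences of contact:

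- IFH contact, no later professional contact, death: trigger met; PI and CI assess.
- IFH contact, then a routine midwife or health visitor contact, death before the next IFH contact: trigger not met.
- IFH contact, then hospital care (with or without IFH advice to seek help), death during that care: trigger usually not met, because hospital staff would normally be the last professionals in contact.
- No IFH contact at all: trigger not met, and no reason for it to be.

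Two limits apply. Advice to seek help does not in itself change who was last in contact; the professional contact that follows does. A routine visit removes a case from the route only until the IFH is next in contact, and section 7.1.2 has IFHs offering daily contact for two weeks and less frequent contact up to eight weeks.

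**3. Are the second and third sequences realistic under this protocol?** Section 7.1.1 describes routine maternity care, and section 7.1.2 adds the intervention to usual care, so professional contacts are interleaved with IFH contacts. Section 9.1 also quotes 38 admissions per 1,000 live births for jaundice, gastroenteritis and feeding difficulties. Treating each planned participant as one live birth:

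- both arms: 2,730 × 0.038 = 103.7, about 104 infants;
- intervention arm: 1,606 × 0.038 = 61.0, about 61 infants.

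These are admissions, not deaths, and they cover three months, whereas IFH support ends at eight weeks. They show only that hospital contact for feeding-type reasons should be expected among supported women.

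**4. Is there another route to a relatedness judgement?**

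- Section 9.1, capture and DMC review: covers all infant deaths and their causes; states no relatedness judgement and no supply of IFH contact history to the DMC.
- Section 9.2: notification only.
- Section 10.2: names an infant death form and mentions an SAE reporting procedure; describes no relatedness step for either.
- Section 13.5: safety analyses for the DMC at least annually; no case-level causality.
- Section 16.6: annual DMC meetings, with an emergency meeting possible if a safety issue is identified; no case-level causality.

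No second route is stated.

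**5. Trigger against definition.** The Definitions table asks whether the event resulted from a research procedure. The trigger asks who was last in contact. An event could satisfy the first and fail the second, so the screen is narrower than the definition and is applied before relatedness is considered.

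**The case against.** The strongest reply is that 9.1 already protects against missed harm. Every infant death and its cause is captured in both arms and reviewed by an independent committee, which can meet urgently and recommend stopping. In a randomised trial, comparing deaths between arms is arguably better evidence than causality opinions from an unblinded PI and CI. The section also justifies light-touch reporting: the support is low risk, its components appear in national guidance, and the cited literature reports no related harms. Case-level review prompted by any IFH contact would take in deaths preceded by no more than one antenatal message.

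Much of this stands. A reader might infer from the trigger that the other deaths are never assessed, or are removed before anyone looks at them. The documents do not support that, because the capture and DMC review carry no last-contact condition. A reader might also say that the trigger contradicts the definition of a related event. It does not: one says what related means, the other says which reports prompt an extra investigation. Nor do the documents show that the deaths outside the trigger are the ones most likely to be related, or that those inside it are mainly unrelated. Finally, 9.1 does not itself say that its route is exclusive. That is read from the absence of another, and the procedures behind the infant death form are not set out.

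What the reply does not remove is the gap. The sponsor judged that some deaths need a relatedness assessment in addition to DMC review, and chose them by order of contact. The protocol gives no reason for that choice. The asymmetry between arms is not new either, since the existing trigger in effect reaches only women who had an IFH.

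**Conclusion.** The point holds in a limited form. An individual relatedness assessment is stated only for infant deaths where an IFH was the last health care professional or feeding supporter in contact with the woman. Deaths that follow IFH support and then another professional contact are captured with cause and reviewed by the DMC, but have no stated relatedness assessment. The last-contact condition and the broader definition of a related event should be reconciled.

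The size cannot be computed. The protocol gives no infant death rate and no information on how often another professional would be the last contact before a death. The count is likely to be small. The conclusion assumes that procedures not shown, such as those attached to the infant death form, do not already contain a relatedness step. If they do, 9.1 need only refer to them. This is a cheap and worthwhile improvement to the safety section and does not affect the primary comparison.

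**What to change.** In 9.1, replace the last-contact condition. Suggested content: for any reported infant death where an IFH had contact with the woman, the local PI reviews the case using the IFH contact log and the CI assesses relatedness, regardless of who was last in contact; the assessment is passed to the DMC alongside the information on deaths that it already receives. Relatedness is then judged against the protocol's own definition.

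The cost is one amended sentence and a few more case reviews over the trial. The contact database in 10.4 and the notification of deaths in 9.2 already supply what is needed, so no new data collection is required. The drawbacks are that these reviews are made unblinded, concern in effect one arm, and will include some deaths where IFH contact was slight. The DMC should therefore read them as case-level information beside the between-arm comparison, not in place of it.
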